4.6.5 Risks associated with exposure to ionising radiation (CT scan and bone scan)

Exposure to ionising radiation carries a risk of deleterious effect, in this case induction of excess cancers in the exposed population. However, it should be noted that risks relating to cancer induction may not be expressed for many years, and are therefore of reduced significance in some patient groups, e.g. those where life expectancy is reduced, or the elderly. In some such groups the cancer induction risk is unlikely to be expressed during the remaining years of life.

4.7. Potential benefits to participants

Additional medical care

Through the schedule of study visit and investigations, including study-specific MRI scans and contact with health professionals, participants in this study will benefit from enhanced level of medical care. This enhanced level of care may facilitate the early diagnosis and management of any disease related complications and/or comorbid conditions should they occur.

Potential anti-tumour activity

Among the population of men with prostate cancer in this study there is as yet no proven clinical benefit from the therapies under investigation. However, checkpoint inhibitor drugs have demonstrated anti-tumour efficacy and clinically significant benefits as single agent therapies in phase III trials against multiple non-prostatic malignancies, including melanoma, non small cell

lung cancer, bladder cancer and renal cell carcinoma. Moreover, results of a small phase II study of anti-PD-1 antibody treatment in metastatic prostate cancer indicate that a short course of checkpoint inhibitor monotherapy can elicit significant anti-tumour activity and a measurable clinical benefit among some patients.

In addition, among men with localised low- and intermediate-risk prostate cancer ChAd-MVA 5T4 vaccination has been shown to elicit immunological responses which are compatible with anti-tumour activity against prostate cancer cells. This effect forms the basis for the ADVANCE study and supports the possibility that combined checkpoint inhibitor therapy and ChAd-MVA 5T4 vaccination might induce enhanced anti-cancer immunity. Such an effect could potentially reduce the patients' risk of recurrence after surgery for localised and locally advanced prostate cancer and delay, slow or prevent disease progression in patients with metastatic disease.

5. RECRUITMENT AND WITHDRAWAL OF STUDY SUBJECTS

5.1. Selection of Participants

Participants will be recruited into either of two cohorts within the study - subjects with operable localised or locally advanced prostate cancer who are planned to undergo radical prostatectomy, or subjects with metastatic prostate cancer who demonstrate disease progression on therapy with second generation anti-androgens (enzalutamide or abiraterone).

Radical prostatectomy group

The subjects recruited will be men over the age of 18 years, diagnosed with low- or intermediate-risk localised or locally advanced prostate cancer and deemed operable and fit to undergo radical prostatectomy by the treating consultant urological surgeon. The number of subjects newly diagnosed with low- and intermediate-risk prostate cancer and selecting radical prostatectomy as their treatment option at the Oxford Churchill Hospital is approximately 5 per month. At the point when the decision has been made to offer radical prostatectomy as one of the potential treatment options, the trial will be introduced to the patient by the existing medical care team during their routine clinic visit, the PIS will be given and permission will be sought for the research team to approach them.

Metastatic prostate cancer groups

Subjects recruited will be men over the age of 18 with a diagnosis of prostate cancer, metastatic to one or more distant sites, who have demonstrated disease progression following anti-androgen treatment with either enzalutamide or abiraterone as a standard of care. Subjects will be identified in the outpatient setting by the existing medical care team during their routine clinic visit, the PIS will be given and permission sought for the research team to approach them. The number of metastatic prostate cancer patients demonstrating evidence of disease progression on enzalutamide is approximately 2 per month at the Oxford Churchill Hospital.

5.2. Informed consent

All patients will sign and date the informed consent form before any study-specific procedures are performed. The information sheet will be made available to the patient at least 24 hours prior to the screening visit. The patient will be fully informed of all aspects of the trial, the potential risks and their obligations. The following general principles will be emphasised:

- Participation in the study is entirely voluntary
- Refusal to participate involves no penalty or loss of medical benefits
- The patient may withdraw from the study at any time
- The patient is free to ask questions at any time to allow him or her to understand the purpose of the study and the procedures involved
- The study involves research of an investigational vaccine and checkpoint inhibitor
- The study involves delaying the patient's surgery by approximately 2 months
- There may be no direct benefit for participating

The aims of the study and all tests to be carried out will be explained. The patient will be given the opportunity to ask about details of the study, and will then have time to consider whether or not to participate. If they do decide to participate, they will sign and date the consent form, which will also be signed and dated by the investigator. One copy will be given to the participant, one copy will be placed in the study file, and the original will be placed in their medical notes.

5.3. Inclusion and Exclusion Criteria

Inclusion Criteria - Radical Prostatectomy groups

The participant must satisfy all the following criteria to be eligible for the study:

- Histologically confirmed adenocarcinoma of the prostate
- Clinically localised or locally advanced disease deemed operable by the treating consultant urological surgeon *i.e.:*
 - Gleason score ≤ 7
 - Local tumour stage $\leq T3c$ and deemed operable
 - No evidence of metastases (Nx/N0 and Mx/M0)
 - No evidence of high grade Gleason 5 disease
 - PSA ≤ 20 ng/ml
- Scheduled for and considered fit for radical prostatectomy
- Absence of any indication to perform urgent surgery that would not allow completion of the study interventions prior to radical prostatectomy

Inclusion Criteria - Metastatic prostate cancer groups

The participant must satisfy all the following criteria to be eligible for the study:

- Histologically confirmed adenocarcinoma of the prostate cancer. Note, any Gleason grade or primary tumour staging at diagnosis is permitted.
- Evidence of at least one distant metastasis based on MRI, CT, PET or bone scintigraphy.
- Established on and suitable to continue with androgen deprivation therapy (ADT) using any luteinizing hormone releasing hormone (LHRH) agonist. LHRH agonist therapy may include goserelin (Zoladex®), leuprorelin acetate (Prostap®) or any other licenced product in this class.
- On treatment with anti-androgen therapy using either abiraterone (Zytiga®) or enzalutamide (Xtandi®) and demonstrating evidence of disease progression at the time of enrolment, defined according Prostate Cancer Working Group 3 Criteria as either:
 - PSA progression as defined by a minimum of 3 rising PSA levels with an interval of ≥ 1 week between each assessment where the PSA value at screening should be ≥ 2 ng/mL *or*;
 - progressive nodal or visceral disease *or*;
 - progressive bone metastases

Upon enrolment in the study, the treatment with abiraterone or enzalutamide will be discontinued.

- An archival specimen of tumour tissue should be available; if not, an on-study fresh tumour biopsy must be obtained prior to the first study treatment.
- Patients who have received chemotherapy following progression on androgen-targeting therapies are eligible
- Satisfactory functional status defined as Eastern Cooperative Oncology Group (ECOG) Performance Status ≤ 1

Inclusion Criteria – All participants

All participants must satisfy all the following criteria to be eligible for the study:

- Males aged over 18 years
- Any antineoplastic therapy, including Radium-223 and limited field radiotherapy must have been completed a minimum of 28 days prior to enrolment.
- Systemic antimicrobial therapy, for any indication, must have been completed a minimum of 7 days prior to enrolment. Baseline laboratory parameters obtained no more than 28 days prior to administration of the first study drug must meet the following criteria:

Laboratory Index	Eligibility threshold
Haematology	
Haemoglobin	≥ 80 g/L
White cell count	≥ 2.0 x10 ⁹ /L
Neutrophils	≥ 1.5 x10 ⁹ /L *
Lymphocytes	≥ 0.5 x10 ⁹ /L
Platelets	≥ 100 x10 ⁹ /L
Clinical Biochemistry	
Renal	
Creatinine Clearance	≥ 40 ml/min by Cockcroft Gault formulation
Hepatobiliary	
Total Bilirubin	≤ 1.5 ULN
ALT	≤ 1.5 ULN
Amylase	≤ 1.5 ULN

* unless established as stable, benign ethnic neutropaenia

- On enrolment, the subject, or the subjects partner, must agree to continuously practice a reliable form of contraception during treatment and for a minimum of 5 months following the final administered dose of nivolumab (Opdivo®). Reliable forms of contraception are:
 - Male sterilisation (Vasectomy)
 - Barrier methods of contraception (condom with or without spermicide)
 - Established use of oral, injected or implanted hormonal contraceptives.
 - Placement of an intrauterine device (IUD) or intrauterine system (IUS).
 - Female sterilisation (Tubal occlusion) or Total abdominal hysterectomy
 - Complete abstinence when this is in line with the preferred and usual lifestyle of the subject. Periodic abstinence, natural family planning and withdrawal are not acceptable methods of contraception.
- Subject is able and willing in the Investigator's opinion to comply with all study requirements
- Subject is able to provide written informed consent

Exclusion Criteria – All participants

The patient may not enter the study if any of the following apply:

- Any prior diagnosis or clinical suspicion of autoimmune disease including, but not limited to, systemic lupus erythematosus, inflammatory bowel disease, vasculitis, Grave's disease and type I diabetes mellitus. Note, subjects with known pre-existing clinically silent positive autoantibodies should not be included (although these will not be assayed at screening unless indicated)
- History of allergic disease or reaction likely to be exacerbated by any component of the vaccine, e.g. egg products

- Other prior malignancy with an estimated $\geq 30\%$ chance of relapse within 2 years. Allowed recent cancers include (but are not limited to) non-melanomatous skin cancer and superficial bladder cancer
- Participation in another research study involving an investigational product or investigational surgical procedure in the 30 days preceding enrolment, or planned use during the study period
- Any prior exposure to checkpoint inhibitor drugs including anti-PD-1, anti-PD-L1, or anti-CTLA-4 monoclonal antibodies or any prior treatment with investigational vaccines
- Administration of immunoglobulins and/or any blood products within the one month preceding the planned administration of the study drugs
- Seropositive for hepatitis B surface antigen (HBsAg)
- Seropositive for hepatitis C virus (antibodies to HCV)
- Any confirmed or suspected immunocompromised state, including but not limited to, asplenia, HIV infection, a history of atypical, recurrent or severe infections, or, regular use (> 14 days) of systemic immunosuppressant medication within the past 6 months (except that lower dosage of prednisolone (< 11 mg per day) are allowable)
- Any history of hereditary angioedema, acquired angioedema, or idiopathic angioedema
- History of anaphylaxis in relation to vaccination or any clinically significant allergic disease likely to be exacerbated by any component of the vaccine or checkpoint inhibitor preparations, as listed in the Investigator's Brochure and SmPC
- Confirmed or suspected recreational drug use or harmful drinking in the last 5 years
- History of a serious psychiatric condition or other circumstances that may be associated with impaired mental capacity
- Evidence of significant clinical disorder or laboratory finding which in the opinion of the investigating physician increases the level of risk to the patient, limits the ability of the patient to participate in the study or impairs interpretation of the study data

Exclusion Criteria – Metastatic prostate cancer groups

The patient may not enter the metastatic prostate cancer arm of the study if:

- The treating oncologist or urological cancer MDT estimates a subject's life expectancy to be ≤ 6 months
- Any active, previously treated, or suspected intracranial or leptomeningeal metastases.

5.4. Concurrent therapies

All concomitant medications and interventions at enrolment and during follow up must be recorded in the study CRF.

Permitted treatments

There are no restrictions on the use of the following therapies:

- Treatment with alpha blockers (e.g. doxazosin, tamsulosin or terazosin) or anticholinergic preparations (e.g. oxybutynin) for relief of lower urinary tract symptoms.
- Non-systemic corticosteroids (i.e. topical, ocular, inhaled, intranasal, and intra-articular preparations) for non-autoimmune disorders are permitted throughout the study.
- Palliative (limited-field) radiotherapy for control of pain metastatic bone pain is permitted, as clinically indicated, throughout the study.

Restricted Treatments

The following therapies and interventions are restricted during the study:

- Systemic corticosteroids are permitted when in conjunction with abiraterone therapy at a dose \leq 10mg oral prednisolone daily (or equivalent).
- Systemic corticosteroids >10 mg oral prednisolone daily (or equivalent) are permitted in the management of immune-related checkpoint inhibitor toxicity only, according to site-specific treatment algorithms.
- Non-investigational vaccines for the prevention of seasonal or travel-associated infections should be undertaken before enrolment wherever possible. Vaccines within the first 6 months of study therapy should be approved by the Investigators in view of the potentially elevated risk of autoimmune reactivity.

5.5. Delay and discontinuation criteria

Discontinuation rules

Treatment with study vaccines and checkpoint inhibitors should be permanently discontinued under the following circumstances:

- On withdrawal of informed consent i.e. the subjects request to discontinue
- Any immune-related checkpoint inhibitor toxicity \geq Grade 3 in severity in the following organ systems:
 - o Dermatological
 - o Gastrointestinal, hepatic or hepatobiliary
 - o Respiratory
 - o Renal
 - o Endocrine
 - o Neurological (apart from headache)
 - o Haematological
- Any infusion reaction of \geq Grade 3 severity

- Any significant clinical disorder, laboratory finding or adverse event, in the judgment of the Investigator makes it unsuitable for the participant to continue study treatment.

Dose delay criteria

Treatment with study vaccine and / or checkpoint inhibitor should be delayed under the following circumstances:

- If the subject has a temperature of > 37.5 °C.
- Any immune-related checkpoint inhibitor toxicity of < Grade 3 in severity, until symptoms have resolved and management with corticosteroids (if indicated) is complete
- Any grade 2 electrolyte disturbance (i.e. abnormalities in serum sodium, potassium, calcium or magnesium), until appropriate correction / replacement has been initiated
- Any significant clinical disorder, laboratory finding, adverse event or intercurrent illness which in the judgment of the Investigator makes it unsuitable for the participant to proceed with treatment.

5.6. Withdrawal criteria

Subjects may be withdrawn from the study early:

- By withdrawing voluntarily
- On the decision of the Investigator
- On the advice of the local safety monitor (LSM)

The Investigator may withdraw the subject for any of the following reasons:

- Any adverse event which results in inability to comply with study procedures
- Ineligibility either arising during the study or retrospectively (having been overlooked at screening)
- Evidence of significant change in disease status such that an alternative care pathway becomes indicated, for example the requirement for salvage radiotherapy following prostatectomy or transition to palliative care in participants with metastatic disease.
- Significant protocol deviation
- Subject non-compliance with study requirements
- Loss to follow up (applies to a subject who does not return for protocol study visits, is not reachable by telephone or other means of communication and/or is not able to be located).

The reason for withdrawal will be recorded in the CRF. If the subject is withdrawn due to an AE, the Investigator will arrange for appropriate specialist management or follow up visits or

telephone calls until the AE has resolved or stabilised. Withdrawn participants will not be replaced.

If a subject withdraws from the study, data and blood samples collected before their withdrawal from the trial will be used/stored unless the subject specifically requests otherwise.

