Checkpoint inhibitor treatment is associated with immune-mediated adverse reactions which may affect any organ system. Current data on the incidence of immune-related toxicities are derived from a number of large phase III clinical trials administering weeks to months of continuous checkpoint inhibitor therapy until disease progression, loss of clinical benefit or unacceptable toxicity, in a range of non-prostate tumour types. This study, however, will make use of a **restricted course of treatment limited to 3 infusions 4 weeks apart for metastatic PCa patients and only 1 infusion for low- or intermediate- risk PCa patients**. The incidence and severity of immune-mediated toxicities following a limited course of 3 infusions four weeks apart is not publically available. However, immune-mediated adverse events may occur at any time from the onset of therapy or after completion of treatment and may not be dose-dependent. Most immune-related adverse reactions, however, are low in severity and resolve with appropriate management, though fatal cases have been reported.

The frequency and median time to onset for the major immune mediated toxicities from pooled phase III datasets are shown in Table 1. These data relate to continuous therapy regimes with repeat nivolumab infusions at 2 week intervals. The incidence of toxicities grade 3 or above is <2% for all organ systems. Importantly, more than 50% of immune-mediated toxicities develop after several weeks of continuous treatment, therefore the frequency and risk of treatment-related adverse events following a restricted course of 3 infusions in this study is anticipated to be considerably lower than during licenced clinical use.

Table 1. Immune mediated adverse events after continuous monotherapy with Nivolumab

Immune-mediated toxicity	Frequency (%) *		Median (range) time to onset (months)	Corresponding number of doses at median time of onset **
	Any severity	Grade 3 or above		
Rash	25.6	0.9	1.4 months(0.0-113.7)	3
Diarrhoea / Colitis	12.6	1.3	1.4 months (0.0-20.9)	3
Pneumonitis	3.0	0.8	3.3 months (0.0-19.6)	7
Liver dysfunction/ Hepatitis	6.4	1.8	1.9 months (0.0-10.4)	4
Renal dysfunction	2.7	0.5	2.3 months (0.0-18.2)	5
Endocrinopathy				
Thyroid disorders	8.5	<0.1	2.8 months (0.0-14.0)	6

Adrenal insufficiency	0.4	0.2		
Pituitary disorders	0.4	0.2		

* From pooled dataset n = 2227 (CA209066, CA209037, CA209067 trials) nivolumab 3mg/kg across tumour types

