8.5. Reporting procedures

Reporting Procedures for All Adverse Events

After an eligible participant is enroled onto the study on receipt of the first study procedure, all AEs occurred within 28 days of study treatment and only grade 3 AEs outside this time window will be reported in the study case report forms (CRF), whether or not attributed to study procedures. AEs may be observed by the Investigators or reported by the participant either spontaneously or during diary card monitoring. All AEs that result in a subject's withdrawal from the study will be followed up, with their consent until a satisfactory resolution occurs, or until a non-study related causality is assigned.

Reporting Procedures for Serious Adverse Events

All serious adverse events (SAEs) occurring after an eligible participant is enrolled onto the study on receipt of the first study intervention, will be reported throughout the trial period. All SAEs will be documented accurately and notification deadlines respected. SAEs will be reported on an SAE Report Form to the Sponsor or the Sponsor's delegated representative (Chief Investigator) and the Study Medical Monitor (SMM), according to the relevant SOP within 24 hours of the Investigator becoming aware of them. SAEs will not normally be reported immediately to the ethical committee(s) and MHRA unless there is a clinically important increase in occurrence rate, an unexpected outcome, or a new event that is likely to affect safety of trial volunteers, in the opinion of the Chief Investigator and/or SMM. In addition to the expedited reporting above, the Investigator shall include all SAEs in the annual Development Safety Update Report (DSUR) report. Any updates to relevant information concerning the SAE that becomes available after the SAE initial report has been sent (outcome, precise history, results of investigations, copy of hospital report, etc) will be forwarded in a timely manner using the SAE Update Report Form. For all deaths, any available post-mortem reports and relevant medical reports will be made available for reporting to the relevant authorities. The Sponsor, or a medically qualified investigator delegated by the

Sponsor, is responsible for commencing, maintaining and completing the SAE Sponsor Report Form. The anonymity of subjects shall be respected when forwarding this information.

Expectedness

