8.6. Procedures to be followed in the event of abnormal findings

Abnormal clinical findings from medical history, examination, urinalysis or blood tests at any point in the study will be assessed as to their clinical significance. If a test is deemed clinically significant, it may be repeated, to ensure it is not a single occurrence and further diagnostic investigations carried out to determine any underlying pathology. If a result or finding is persistent or clinically significant, the subject will be informed and appropriate medical care arranged as appropriate and with the permission of the subject. Decisions to exclude the subject from enrolling in the trial or to withdraw a subject from the trial will be at the discretion of the Investigators, following procedures for adverse events as described above.

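### Section 5.6 lets the investigator withdraw an already dosed man from the whole study, and nothing then keeps him in scheduled follow-up

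*Protocol*

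**What the plan says.** Stopping treatment and leaving the study are separate rules in the protocol. Section 5.5 lists when vaccine and nivolumab are delayed or permanently stopped. Section 5.6 concerns early withdrawal from the study. It says the investigator may withdraw a man for several reasons, among them "Ineligibility either arising during the study or retrospectively (having been overlooked at screening"). Other grounds in the same list are an adverse event that leaves him unable to comply with procedures, a change in disease status that calls for another care pathway (such as palliative care in metastatic disease), and a significant protocol deviation. Section 8.6 likewise says that decisions "to withdraw a subject from the trial will be at the discretion of the Investigators".

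On what happens next, section 5.6 arranges care, visits or calls when an adverse event was the reason, until that event resolves or stabilises. Section 8.5 says that adverse events leading to a man's "withdrawal from the study will be followed up, with their consent until a satisfactory resolution occurs". Section 5.6 also says that data and blood samples collected before withdrawal are used unless the man asks otherwise, and that withdrawn men are not replaced.

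Section 6.1 counts a man as enrolled only once he has had the first vaccination, and it has ongoing eligibility reviewed at each later visit.

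**The concern.** A dosed man found ineligible, or whose disease has moved on, still contributes information on safety and efficacy. Stopping further doses may be right for him. Ending his assessments is a different decision, and the protocol allows it without saying that any scheduled assessment continues.

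The loss need not be random. Some ineligibility has nothing to do with outcome, for example a contraception lapse or an overlooked product exposure such as "Administration of immunoglobulins and/or any blood products within the one month preceding the planned administration of the study drugs". Change in disease status is the most outcome-linked ground, because a man moved to palliative care is likely to be a non-responder with a poor prognosis. In Group 2, ECOG status above 1 could act in the same way if treated as ineligibility arising later.

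Safety is a primary endpoint in both groups, and section 7.1 counts adverse events up to 12 months after treatment. Section 4.6.4 warns that "immune-mediated adverse events may occur at any time from the onset of therapy or after completion of treatment". PSA and ctDNA response are primary in Group 2. Radiographic progression-free survival and overall survival are secondary there.

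**Working it through.** **Step 1. Does any text keep a withdrawn man in follow-up?** Four places come close.
- Section 4.4 sets follow-up at 6 months for Group 1 and 12 months for Group 2. It does not mention withdrawn men.
- Section 8.5 has SAEs reported for the duration of the trial. This is a reporting duty and sets no visits after withdrawal.
- Sections 5.6 and 8.5 follow the adverse event that led to withdrawal. They do not cover a man withdrawn for ineligibility, disease change or a deviation, and they do not cover events that start later.
- Section 5.6 retains earlier data. It adds nothing after withdrawal.

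None of these provides scheduled AE, PSA, ctDNA, imaging or survival assessment after withdrawal.

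**Step 2. What would a Group 2 man lose?** Inputs are from Appendix 1: post-baseline PSA at V2 to V13 (12 values) and post-baseline ctDNA at V3, V5, V7 and V11 (4 draws). V11 is taken as week 24, being the visit with the 6-month radiology. Samples at the withdrawal visit are assumed taken.

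| Withdrawn at | PSA values held (of 12) | ctDNA draws held (of 4) | Week-24 sample |
|---|---|---|---|
| Week 4 (V3) | 2 | 1 | none |
| Week 8 (V5) | 4 | 2 | none |
| Week 12 (V7) | 6 | 3 | none |
| Week 16 (V9) | 8 | 3 | none |

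Section 6.2 schedules Group 2 imaging at baseline, 6 months and 12 months, so a man withdrawn by week 16 also has no scheduled post-baseline scan.

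**Step 3. Size on the response rates.** The protocol gives no withdrawal figure, so 1 or 2 men is an assumption.
- 24-week rate, share unknown = k/24: 1/24 = 4.2 points; 2/24 = 8.3 points.
- Any-time rate, share unknown = (1 − r) × k/24, where r is the fraction who had already responded. Assume r between 0 and 0.25, the upper value borrowed from the target rate in section 9.1. One man: 0.75 × 1/24 = 3.1 to 4.2 points. Two men: 0.75 × 2/24 = 6.3 to 8.3 points.

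**Step 4. Size on late safety.** Section 8.5 records all adverse events within 28 days of treatment and, beyond that, only grade 3 events and SAEs. The late loss therefore concerns those. Table 1 in section 4.6.4 gives grade 3 or above frequencies of 0.9, 1.3, 0.8, 1.8, 0.5, under 0.1, 0.2 and 0.2 per cent. Taking the thyroid figure as 0.1, they sum to 5.8 per cent, or about 0.06 listed events per man under continuous nivolumab alone. Only part of this would fall after withdrawal, and section 4.6.4 expects less with the restricted course. The combination with vaccine is untested, so the figure is only a guide.

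**The case against.** The strongest reply is that the clause is permissive and may seldom be used. That stands: nothing shows that investigators would use it to end follow-up, and the number of men is unknown.

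A reader might infer a stronger point: that men with immune toxicity would be removed systematically, because the exclusions include "Any prior diagnosis or clinical suspicion of autoimmune disease" and "regular use (> 14 days) of systemic immunosuppressant medication within the past 6 months", and eligibility is reviewed again at each visit. The documents do not support this. Section 5.4 expressly permits systemic steroids above 10 mg of prednisolone daily for checkpoint inhibitor toxicity. Section 5.5 handles that toxicity by delaying doses or stopping treatment. For new clinical or laboratory findings at a visit, section 6.1 states that dosing may be postponed under section 5.5. Steroid treatment of toxicity is thus foreseen on study and should not be treated as ineligibility.

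A reader might also try to size the problem by counting the eligibility reviews after the last dose, or by modelling a shift in the survival estimate. Neither measures this clause. A scheduled review is not a withdrawal, and a survival shift would depend wholly on invented numbers of withdrawals and deaths.

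Sections 4.4 and 8.5 are fair counter-texts, and part of the safety loss is covered because an adverse event that causes withdrawal is followed. Late events in men withdrawn for other reasons are not. How withdrawn men enter the denominators can be left to the SAP; whether they are still observed cannot.

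**Conclusion.** The point holds as a minor one. Section 5.6 allows study-level withdrawal of treated men on several investigator-decided grounds, and the protocol then states follow-up only for a causative adverse event. Ineligibility is one of these grounds; change in disease status is the most likely to be linked to outcome.

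Each Group 2 man withdrawn by week 16 leaves 4.2 points of the 24-week rate unknown and, under the stated assumption, 3.1 to 4.2 points of the any-time rate. He also leaves imaging and survival follow-up. The late safety loss per man is probably a few hundredths of a listed grade 3 or higher event. These sizes rest on the Appendix 1 schedule, on V11 being week 24, and on an assumed count of 1 or 2 men. The text does not show that such withdrawals will be common, that they are required, or that they will bias a result in a known direction.

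**What to change.** Add to section 5.6: where the investigator acts because of ineligibility, an adverse event, a change in disease status or a protocol deviation, this is a reason to stop study treatment only. The man stays in scheduled AE, PSA, ctDNA, imaging and survival follow-up, as applicable to his group, unless he withdraws consent. If visits are not feasible, at least SAEs and survival status are collected by telephone or from the notes. It would help to add that steroid treatment of checkpoint toxicity under section 5.4 does not count as ineligibility.

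Nothing else has to change. The eligibility reviews in section 6.1 and Appendix 1 can stay, since they would no longer end follow-up, and no extra contraception question is needed. The cost is a few lines of wording. No new visit or sample type is added, but men who stop treatment would carry on with visits already scheduled, which is some burden for them.
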